Follow-up	 Start: Date(s)^a participant meets all eligibility criteria (baseline survey) End: Earliest of the following events: Outcome event, Loss to follow-up (e.g., non-response of two consecutive surveys)^b, Participant withdrawal, Deviation from assigned treatment strategy (e.g., treatment change), Loss of eligibility, and Administrative end of study (one-year of follow-up).

Abbreviations: HCP = Healthcare Practitioner; HIPAA = Health Insurance Portability and Accountability Act; MVA = motor vehicle accident

^a Participants may meet eligibility criteria at numerous calendar dates. The study design permits participants to enter the analytic cohort repeatedly (i.e., at each calendar date that participant is study-eligible) during the participant enrolment period (see Section 9.1 for a detailed description).

^b Participants who are lost to follow-up will be censored at 67 days following the opening of their last survey (as participants are allotted 7 days to answer each monthly survey).

Data on potential confounders, treatments received, and occurrence of the outcome event over follow-up will be ascertained with a series of monthly surveys administered sequentially over the 12 months following enrolment (see Section 9.3.4). The initial (baseline) survey will collect additional information on potential confounders and treatments in the year prior to enrolment (see Section 9.3.3). To align with the primary research objective, only the first occurrence of MVA since study enrolment will serve as the outcome of interest for primary analysis.

Given that patients may be eligible for study entry at multiple calendar times, and that their eligibility may fluctuate over the course of the study (e.g., due to loss of access to a vehicle or driving privilege for one or more months), a 'nested trial' approach will be implemented (Danaei et al. 2013; Danaei et al. 2018). In this approach, the raw survey data collected from participants will be transformed into an analytic dataset as follows:

- 1. Select participants who are study-eligible on the first calendar day of study recruitment and assign their analytic 'time zero' to this day.

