- 2. Assign each participant to one of the three treatment strategies of interest (see Table 1) based on their self-reported use of prescribed anti-migraine medications in the prior 30 days: participants who used lasmiditan at least once (Lasmiditan Group), participants who used another prescribed acute anti-migraine medication (includes, but is not limited to, triptans, ubrogepant [Ubrelvy], rimegepant [Nurtec], zavegepant [Zavzpret]; see Annex 3 for the complete list) at least once and did not use lasmiditan (Other Acute Medications Group), and participants who did not use any prescribed acute anti-migraine medication

(No Acute Medication Group). The self-reported use of prescribed preventive antimigraine medication will not be considered for treatment group classification.

- 3. Collect and record each participant's self-reported and calculated confounder history prior to their analytic 'time zero' (see Section 9.7 for potential confounders of interest).
- 4. Define follow-up for each participant from analytic 'time zero' until the earliest of the following: outcome event, loss to follow-up (day 67 of non-response, corresponding to non-response on two consecutive surveys), participant withdrawal, deviation from assigned treatment strategy (e.g., treatment switch), loss of eligibility, or administrative end of study (one-year of follow-up).
- 5. Generate a counting-process formatted dataset for this 'nested trial' derived from longitudinal treatment, outcome, and confounder information assessed in Steps 1-4 (see Section 9.7.2.2.2.1 for example data structure).
- 6. Repeat Steps 1-5 above for each sequential calendar day in which participants will be recruited into the survey study.
- 7. Bind all datasets produced in Step 5 by row. This will serve as the analytic dataset for the primary analysis (see Section 9.7.2.2.2.1 for example data structure).

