9.3.4 Follow-up Variables

The following additional variables will be collected every 30 days during a 12-month period of follow-up for analysis of the primary and secondary objectives:

Dynamic eligibility variables

- Possession of an active driver's licence over the past 30 days,
- Access to a motor vehicle over the past 30 days,
- Have driven at least once in the previous 30 days, and
- Resides in the US over the past 30 days.

Medication use, migraine experience, and the use of anti-migraine medication in the past 30 days

- Migraine experience over the past 30 days: number of migraine attacks, impact of migraine on daily life),
- Use of acute and preventive anti-migraine medications over the past 30 days (medications names, dose for lasmiditan),
- Use of concomitant medications potentially associated with MVA risk (including antihistamines, antidepressants, benzodiazepines, beta-blockers, opioids, anti-seizure medications, antipsychotics, sleeping pills including sedatives and hypnotics) within the last 30 days, and
- New comorbidities declared in the last 30 days (including hypertension, hypotension, musculoskeletal diseases, ophthalmological diseases, insomnia, anxiety, diabetes, depression, other psychiatric disease, chronic insomnia, chronic fatigue syndrome, seizure disorders).

Driving characteristics and experience of MVAs for which the participant was the driver

- Change of ZIP code of residency,
- Approximate number of miles driven in the past 30 days, and
- Number and dates of self-reported MVAs for which the participant was the driver occurring during the past 30 days, details and circumstances of these MVAs (details provided below).

Details on self-reported MVAs for which the participant was the driver in the last 30 days

- Location of MVA,
- Severity of the accident (approximated by the extent of motor vehicle and property damages),
- Speed of the motor vehicle driven by the participant,
- Other vehicle(s) and/or persons involved (i.e., pedestrian, cyclist, motorcyclist, car, other vehicle),

Non-Interventional Protocol

- Perceived fault and reasoning for the accident,
- Seriousness of related injuries for any persons involved in the MVA:
 - Slightly injured: minor character of injury not requiring medical treatment such as a sprain (including neck whiplash injury), bruise or cut which are not judged to be severe, or slight shock requiring roadside attention, and

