9.7.2.2.2 Primary Statistical Analysis

9.7.2.2.2.1 Data Structure and Notation

The data structure generated from the procedure illustrated in Section 9.1 will take on the general form shown in Table 5. As illustrated, each row of the data will represent an observation of a given participant at the kth interval of follow-up for the mth 'trial.' The treatment indicator A_k will take on one of three values corresponding to the treatment strategies of interest (see Section 9.1) and will be constant for a given participant within a given mth trial. Treatment history, denoted A_{k-1} , is the treatment the participant received in the prior (k-1) interval. A vector of baseline covariates, denoted L_0 , will take on fixed values across all 'k' intervals of a given participant's 'participation' in an mth trial. A vector of time-varying covariates, denoted L_k , will take on their recorded values at time 'k' in a given participant-trial. The event indicator, denoted D_{k+1} , will take on a value of one if the event occurred in the subsequent (k+1) interval, or a value of 0 otherwise (e.g., censoring).

In the data structure, the number of rows for each participant in a given mth trial will correspond to the length of follow-up. For example, in Table 5, Participant 3 participated in nested trial 7 and nested trial 9. This participant was followed-up for four intervals in trial 9 and experienced the outcome event in the 4th interval of follow-up. Notably, treatment information recorded in the 4th interval of follow-up is discarded because it is unknown whether treatment was administered before or after the outcome event within that interval. This is because the surveys only collect information and treatment data at the 30-day level.

Participant ID	Trial No. (m)	Follow -up (k)	Treatment (A _k)	Treat Hx (A _{k-1})	Baseline Covariate (L ₀)	Time- Varying Covariate (L _k)	Outcome (D _{m+k+1})	Censor (C _{m+k+1})
1	45	0	0	0	0	0	0	0
1	45	1	0	0	0	1	0	0
1	45	2	0	0	0	0	0	1
2	34	0	2	2	1	0	0	0
2	34	1	2	2	1	1	1	0
3	8	0	1	1	0	1	0	0
3	8	1	1	1	0	0	0	1
3	9	0	0	1	1	0	0	0
3	9	1	0	0	1	0	0	0
3	9	2	0	0	1	1	1	0

 Table 5.
 Generalised Longitudinal Data Structure for the Final Analysis

9.7.2.2.2.2 Statistical Models

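### Nested trials open on every recruitment day and assign by use in the prior 30 days, but that window is observed on only about 4% of a participant's possible time zeros

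*Protocol*

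**What the plan says.** Three rules in Section 9.1 define the trial grid.

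- Step 2 assigns each participant to a strategy "based on their self-reported use of prescribed anti-migraine medications in the prior 30 days".
- Step 6 reads: "Repeat Steps 1-5 above for each sequential calendar day in which participants will be recruited into the survey study".
- Table 1, footnote a, lets a participant "enter the analytic cohort repeatedly (i.e., at each calendar date that participant is study-eligible) during the participant enrolment period".

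The measurement schedule is coarser. Section 9.3.4 states that "additional variables will be collected every 30 days during a 12-month period of follow-up", and the medication item is "Use of acute and preventive anti-migraine medications over the past 30 days". Attack counts, miles driven, licence, vehicle access and residence use the same look-back. No date of acute-drug use is listed outside the accident items. Section 9.7.2.2.2.1 confirms that "the surveys only collect information and treatment data at the 30-day level".

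Other passages describe entry differently. The follow-up row of Table 1 ties the start to the baseline survey. The switching example in Section 9.1 has the participant contributing to two trials. Table 5 shows Participants 1 and 2 in one trial each and Participant 3 in two.

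**The concern.** A nested-trial design is chosen so that eligibility, assignment and covariate history are all fixed at the same time zero. That needs the assignment window to be observed on each day a trial opens.

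Take a participant and a trial opening on day 45 after baseline. Step 2 needs use over days 15 to 45. The day-30 survey covers days 0 to 30 and the day-60 survey covers days 30 to 60, so neither gives the required window. The programmer must either carry day 30 forward, with exposure and covariates 15 days old, or look ahead to day 60, which brings post-time-zero information into assignment. The protocol does not say which. Two programmers could build different primary datasets from the same surveys.

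**Working it through.** The protocol states no figure on this point, so there is none to reproduce. The check counts time zeros.

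**Inputs.** Enrolment lasts 6 months (Section 9.2.4.5), taken as 180 days. Surveys fall at baseline and every 30 days (Section 9.3.4). Entry is on every eligible day to the end of enrolment (Step 6, footnote a). Assumed: enrolment spread evenly over the period, full response, continuous eligibility.

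**Time zeros per participant.** One enrolled with r days left has r possible time zeros.
- Sum over r = 1 to 180: 180 × 181 / 2 = 16,290. Mean: 16,290 / 180 = 90.5.
- Survey-day time zeros: 30 × (1+2+3+4+5+6) = 630. Mean: 630 / 180 = 3.5.
- Share on a survey day: 630 / 16,290 = 3.9%, so **96.1%** have no report for the Step 2 window. A 184-day period gives 92.5 time zeros and the same 96.1%.
- The last report is on average 13.7 days old. It is more than 7 days old at 70% of time zeros and at least 15 days old at 46%.

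**Wrong group at time zero under carry-forward.** Let use follow a Poisson process with λ uses per 30 days (assumed; the protocol gives no rate). With g days since the survey, the reported and required windows share 30 − g days. Any-use status differs between them with probability

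2·e^(−λ)·(1 − e^(−λg/30)).

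Averaged over g = 0 to 29:

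| λ | Wrong at time zero |
|---|---|
| 0.25 | 17% |
| 0.5 | 25% |
| 1 | 26% |
| 2 | 15% |
| 4 | 3% |

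Simulation over a range of assumed rates gave about 2 to 27%. With entry on survey dates the figure is 0 by construction.

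**Mislabelled person-time.** Simulated with a 184-day enrolment, carry-forward, and censoring at the survey that reveals a change. The figure is the share of trial person-time whose label differs from true prior-30-day status.

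| λ | Daily entry | Survey-date entry |
|---|---|---|
| 0.25 | 13.9% | 13.5% |
| 0.5 | 26.0% | 24.0% |
| 1 | 26.5% | 24.8% |
| 2 | 10.1% | 10.2% |
| 4 | 1.5% | 1.5% |

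The two schemes barely differ here. In further simulation under assumed rates the rate ratio mostly moved by less than about 0.1 between them. Filling from the next survey instead of carrying forward moved it by about 0.1 to 0.4 in several scenarios where the hazard was raised on the day of use.

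**Table 5.** Trial numbers 34 and 45 exceed both 6 months and about 26 weeks of enrolment, so they fit only a daily index. On that index Participant 3 changes treatment between trials 8 and 9, consecutive days. Someone enrolled on day 1 has no follow-up survey until day 31, so the surveys could not show that change. The table is only illustrative, but it shows that grid and data do not match.

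**The case against.** The strongest reply is that daily entry does not cause the main exposure error. A person who changes drug just after a survey keeps the old label until the next survey under either scheme, and Section 9.9.2 already discloses that status may be misclassified for this reason. This stands, and the person-time table supports it. A reader might infer that daily entry sends switchers' accidents to the wrong group and that survey-date entry would cure this, or that the hazard ratio is materially biased by the grid. Neither follows. Most of the late-detected error remains after the change.

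A reader might also infer that the plan fills gaps from the next survey. Nothing says so; Steps 2 and 3 look backwards. The point is only that no rule excludes it.

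An out-of-date report is not always wrong. Stable frequent users and stable non-users keep the right group.

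If entry occurs only at baseline and at a survey reporting a change, as Table 1's start and the switching example suggest, the 96% does not apply. That reading contradicts Step 6 and footnote a, so the conflict itself needs resolving.

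The remaining defences do not reach the point:
- Last observation carried forward is stated for non-response (Section 9.7.2.2.2.3), not for ordinary days between answered surveys.
- Contingency 4 may widen the follow-up interval k to save computing time; it leaves the daily trial start alone.
- The disclosure in Section 9.9.2 concerns the order of treatment and outcome during follow-up, not assignment at time zero.
- The bootstrap handles correlation from repeated entry, not wrong assignment.
- A derivation rule could sit in the SAP, but the daily grid and the 30-day window are fixed in the protocol and are incompatible there.

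**Conclusion.** The concern holds in limited form. As written, Step 2 cannot be carried out on about 96% of the time zeros that Step 6 and footnote a create, and the protocol contradicts itself on how often a participant enters. That share follows from the 6-month enrolment and 30-day surveys, with even enrolment and full response assumed. The share of entries in the wrong group at time zero, roughly 2 to 27% under carry-forward, rests wholly on assumed Poisson use rates and should be read as a range. It counts entries, not accidents or person-time, and does not measure bias in the hazard ratio. What is at stake is an assignment rule that can be executed and reproduced, with exposure, covariates and eligibility aligned at time zero.

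**What to change.** Amend Step 6 and Table 1 footnote a so that a participant may enter a nested trial only on a completed-survey date: baseline, then each 30-day survey within the enrolment period. A skipped survey creates no entry. Index trials by the calendar week or month of that date, which still allows for seasonality, and set k to 30 days. Bring Table 1's start of follow-up, the switching example and Table 5 into line.

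The cost is wording and simpler programming. Mean entries per participant fall from about 90.5 to 3.5 (about 26-fold), which also eases the computing problem behind Contingency 4. No observable switch is lost, because switches are seen only at surveys. The condition that event risk per interval stays below 8% is comfortably met: Table 3's higher risk of 5.9% a year is about 0.5% per interval (5.9 / 12). The downsides are slightly coarser calendar indexing and no use of the accident's exact date within an interval. The 7-day completion window remains, so time zero should be defined as the completion date. The late-detection limitation in Section 9.9.2 should stay.

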The 'nested trial' approach has several distinctive advantages. First, it permits greater statistical power by leveraging information following treatment changes in participants over follow-up. For example, if a participant switches treatment strategy from lasmiditan to other prescribed acute antimigraine medication, that participant will contribute person-time to two separate 'trials' (each associated with a single treatment strategy), provided they remain study-eligible. Second, the approach allows the investigator to specify precise and dynamic treatment strategies of interest for comparison, while accounting for potential confounders that have changed since baseline enrolment in the survey study. Third, seasonality of MVA can be accounted for as data within each 'nested trial' is aggregated by calendar time. Fourth, time-varying and time-dependent factors can be accounted for easily with the data structure generated by this approach, including dynamic study eligibility and evolving confounder histories.

Self-reported survey data on prescription migraine medication use (acute and preventive) will be compared with pharmacy data (including prescribed drug and dosage), obtained via linkage with ExamOne ScriptCheck (additional information in Section 9.4.3) to describe concordance.

Participants for this study will be recruited through healthcare practitioner (HCP) referrals. This study will utilise IQVIA Primary Intelligence Research Service (PIRS) to identify and recruit HCPs providing care to the population of interest into a network of referring providers. The HCPs who opt into the study will be able to refer potentially eligible and interested participants with migraine.

The study comprises 2 phases: Phase 1 includes development activities for surveys planned to be administered during Phase 2; while Phase 2 includes prospective follow-up of study participants as well as validation of self-reported prescription medication data for a subset of participants in each treatment group. The study will be administered by one central virtual site managed by IQVIA and a central principal investigator (PI). Using a central PI delivery model is designed to leverage

one PI to provide oversight on the participants' rights, safety, and welfare, and ensure data quality and integrity. Additional details are described below.

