9.2.4.5 Study Duration

The study preparatory period is estimated to last about 6 months, consisting of initial survey development, followed by survey development interviews (Phase 1) to develop, refine and validate the survey questions among 9 participants, and implement any changes based on survey feedback from Phase 1. Subsequently, participants of the prospective study (Phase 2) will be recruited during a 6-month enrolment period, from the date of first participant being enrolled. Data will be collected for a 12-month follow-up from baseline (see Figure 2).

The extraction of prescription claims data for linkage will operationally be performed twice: following the recruitment of the last participant and following the completion of the last survey by the last study participant.

Abbreviations: HRS = Health Research Space; PIRS = Primary Intelligence Research Service.

Figure 2. Study duration.

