9.5 Study Size

According to the US Department of Transportation data through 2021 (US DOT [WWW]), approximately 3% of licenced drivers in the US have motor vehicle crashes during a year; therefore, approximately 3% of participants are expected to have an accident during the 12 months follow-up. This incidence rate is restricted to crashes involving either the car insurance or the police and might be slightly different than the incidence of MVAs self-reported by drivers.

Due to the lack of clear evidence for elevated incidence of MVAs in individuals with migraine compared to the general population, it is assumed that the incidence of MVAs in the general population can be expected in any of the comparison groups (3% per year). A sample of 793 participants per treatment group would provide 80% power at 5% level of significance for detection of a hazard ratio (HR) of 2.0. Given this is a safety study, no alpha correction method will be used. In order to achieve this sample size, an additional 20% will be targeted for enrolment in anticipation of participant dropout (992 per treatment group). A HR of 3.0 could be detected with a minimum of 397 participant after attrition, assuming an MVA rate of 3% in the lower risk group. Thus, a number of 1000 participants per treatment group, is targeted to be enrolled into the study. Due to a limited source population of lasmiditan-treated patients, challenges are anticipated for the recruitment of participants in the Lasmiditan Group.

If a sufficient number of participants treated with lasmiditan is enrolled, prospective follow-up and a comparative analysis will be executed as part of the final analysis (See Section 9.7.2.2).

If the required sample size is not achieved in the Lasmiditan Group and/or the number of incident MVA in the study period is insufficient to provide meaningful comparison between Lasmiditan Group and comparator groups (Other Acute Medication Group and No Acute Medication Group), unadjusted incidence rates of MVAs in each treatment group with precision estimates will be provided as primary analysis (see Section 9.7.2.2.2.2) and descriptive statistics will summarise participants characteristics, treatment patterns, driving patterns and self-reported MVAs experience through the 12-months of follow-up period.

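### Nested trials open only during the 6-month recruitment window, which contradicts the stated gain from treatment changes over follow-up; separately, the sample size makes no allowance for censoring at treatment change

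*Protocol*

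**What the plan says.** Section 9.1 builds the primary dataset in seven steps. Step 2 assigns a strategy from use in the prior 30 days. Step 4 ends follow-up at, among other things, "deviation from assigned treatment strategy (e.g., treatment switch), loss of eligibility". Step 6 reads "Repeat Steps 1-5 above for each sequential calendar day in which participants will be recruited into the survey study". Table 1 footnote a lets a participant enter the analytic cohort repeatedly, "i.e., at each calendar date that participant is study-eligible) during the participant enrolment period".

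Section 9.2.4.5 gives the calendar: participants "will be recruited during a 6-month enrolment period, from the date of first participant being enrolled", and "Data will be collected for a 12-month follow-up from baseline".

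The paragraph on advantages in Section 9.1 says of the approach that "it permits greater statistical power by leveraging information following treatment changes in participants over follow-up". Its example is a participant who moves from lasmiditan to another acute drug and so contributes to two trials. The only condition given is continued eligibility; the enrolment window is not mentioned. The dagger note in Section 9.2.1 keeps temporarily ineligible participants in the study because their eligibility may return.

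Section 9.5 states: "A sample of 793 participants per treatment group would provide 80% power at 5% level of significance", for a hazard ratio of 2.0 and a 3% comparator risk. An allowance of 20% for dropout brings this to 992.

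**The concern.** Two parts of Section 9.1 give different rules for the same event. Under Step 6 and footnote a, a participant whose category changes after recruitment closes is censored in the current trial and has no later trial to enter. Under the advantages paragraph, that participant contributes to a second trial. An analyst cannot follow both. The same problem affects someone who loses vehicle access and regains it after the window closes: Section 9.2.1 keeps that person in the study, but no trial remains to re-enter.

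The exposure affected is the scarce one. Section 9.5 expects difficulty in recruiting lasmiditan users, yet a comparator participant who first reports lasmiditan after recruitment closes adds no lasmiditan time. The fallback analysis has the same problem, because Section 9.7.2.2.2.2 calculates the crude incidence rates from the same person-time-trial dataset.

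A second, separate gap is in Section 9.5. The primary analysis censors at treatment change, but the sample size is calculated as if nobody changes.

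**Working it through.** **Reproducing the plan's figure.** Inputs from Section 9.5: HR 2.0, comparator 12-month risk 3%, 80% power, 5% significance (taken as two-sided), dropout 20%.

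- Freedman events: (1.96 + 0.8416)² × ((1 + 2)/(2 − 1))² = 7.849 × 9 = 70.64.
- Lasmiditan-group risk: 1 − 0.97² = 5.91%.
- Participants per group: 70.64 / (0.0300 + 0.0591) = 792.8, rounded up to 793, which matches.
- With dropout: 793 / 0.80 = 991.25, rounded up to 992, which matches.

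So 793 is a two-group calculation with full 12-month risk. It contains neither re-entry time nor censoring at treatment change.

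**Time after the last trial can open.** Take enrolment at month e, uniform on 0 to 6. Of the 12 follow-up months, 6 − e fall inside the window and 6 + e after it. The mean of 6 + e is 9, and 9/12 = 75%.

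**Effect of the written rule.** The protocol gives no rate of treatment change, so the monthly rate s is an assumption. Further assumptions are a constant rate, balanced switching between groups, immediate re-entry while the window is open, none afterwards, and events proportional to person-time.

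- Months kept, averaged over e: mean of (6 − e) + (1 − exp(−s(6 + e)))/s, which equals 3 + [1 − (exp(−6s) − exp(−12s))/(6s)]/s.
- Example, s = 0.10: 3 + [1 − (0.5488 − 0.3012)/0.6]/0.10 = 3 + 5.87 = 8.87 months, and 8.87/12 = 73.9%.
- Events at 793 per group with nothing lost: 793 × 0.0891 = 70.66. At s = 0.10: 70.66 × 0.739 = 52.2.
- Power: Φ(√events/3 − 1.96). At 52.2 events: Φ(2.41 − 1.96) = 67.3%.

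| Assumed change per month | Person-time kept | Events | Power, HR 2.0 | Needed per group for 80% (793 / share kept) |
|---|---|---|---|---|
| 0% | 100% | 70.7 | 80.0% | 793 |
| 0.5% | 98.3% | 69.4 | 79.3% | 807 |
| 1% | 96.6% | 68.3 | 78.6% | 821 |
| 2% | 93.4% | 66.0 | 77.3% | 849 |
| 5% | 85.0% | 60.1 | 73.3% | 933 |
| 10% | 73.9% | 52.2 | 67.3% | 1072 |
| 20% | 59.4% | 41.9 | 57.9% | 1336 |

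If trials could open throughout follow-up, the same assumptions keep all the person-time: about 70.7 events and 80.0% power at every rate. No row includes a loss from inverse probability weighting or from temporary ineligibility.

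**The case against.** Several stronger readings are tempting, and the protocol does not support them.

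- A reader might infer that the entry rule removes person-time on which the stated 80% power rests. It does not: 793 reproduces exactly with no re-entry time in it. What lowers power is censoring at treatment change, which Section 9.5 omits. Re-entry would offset that loss, and the window limits how much.
- A reader might take the 75% as lost. Participants who never change category keep all their time.
- A reader might count only each participant's first treatment spell. At 5%, 10% and 20% change per month that gives 68%, 57% and 41% power, but the plan does allow re-entry during the window, so these figures are too low.
- A reader might assume that a month without lasmiditan is a deviation, and hence that changes are frequent. Step 2 uses the 30-day look-back to assign the strategy at time zero. Deviation is described only by example, and the protocol does not settle whether a month without use counts. Adding another acute drug to lasmiditan is not a deviation under Table 1.

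The restriction may also be deliberate. The protocol gives no reason for it, but it leaves anyone who re-enters with at least about six months of planned follow-up, which suits a one-year risk aim. Time before a late change still counts, accidents after it remain in the descriptive analyses of Section 9.7.2.3, and censoring weights address selection. Section 9.5 already foresees too few accidents and falls back to unadjusted rates.

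These points limit the size of the concern, but the contradiction remains. The SAP is not at hand. It may define deviation, but the protocol would still state two incompatible rules. Short late trials are not a serious drawback in a pooled hazard model.

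**Conclusion.** The point holds in two parts.

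First, Step 6 and footnote a contradict the switcher benefit claimed in Section 9.1 and fit badly with the dagger note in Section 9.2.1. This rests on the text alone. The 75% figure additionally assumes uniform enrolment.

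Second, the 793 per group makes no allowance for censoring at treatment change, and the 20% for dropout cannot also cover it. The size of this gap depends on a rate the protocol does not give. At 0.5% to 2% per month it is small (about 2% to 7% of person-time, power 79% to 77%). At 5% it is moderate (15%, power 73%). At 10% to 20% it is large (26% to 41%, power 67% to 58%). These figures assume balanced switching and come before any loss from weighting; unbalanced switching was not examined.

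**What to change.** Reword Step 6 and Table 1 footnote a so that an eligible participant can enter a new nested trial at each completed survey throughout follow-up, as long as a further survey interval remains. That brings the algorithm into line with the advantages paragraph in Section 9.1 and with Section 9.2.1. If the window limit is intended, give the reason and restrict the claimed power gain to changes during recruitment.

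Restate Section 9.5 in required events (about 71 for HR 2.0 by the formula used), with power over a stated range of treatment-change rates, including zero.

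The cost is wording. The monthly surveys in Section 9.3.4 already record treatment and eligibility, so no new data are needed. The dataset gains correlated rows and some short late trials. The planned bootstrap handles the correlation, and the follow-up and trial terms in the model accommodate the late entries. The stated power becomes less favourable.
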